5. CHANGES TO PLANNED ANALYSES

The language in the SAP will supersede the language in the protocol should there be a discrepancy.

The primary analysis will be repeated for all visits using observed data (without imputation) for both mITT and PP populations. These results will be provided in sensitivity analyses section.

The difference between two OTX-CSI hydrogel formulations as well as the difference between two HV formulations will not be studied. HV formulations will not be combined.

Wilcoxon rank sum test will be used only to analyze LOCF and observed data.

For Eye Dryness Severity and Eye Dryness Frequency, as well total Corneal Fluorescein Staining (tCFS) and its sub-region the main analysis will be based on MCMC MI and sensitivity analyses will be done using LOCF, observed data, and FCS.

For the first secondary efficacy endpoint analysis, for the main analysis, the two groups of change from baseline in Schirmer test (\geq 10 mm vs <10 mm) at visit 7 will be compared between treatment groups using the logistic regression and for the sensitivity analyses, the groups will be compared using LOCF and observed data by Fisher's exact test; Clopper-Pearson method will be used to calculate 95% confidence interval of the proportion of subject with change from baseline in Schirmer Test \geq 10 mm; to calculate 95% confidence interval of the proportion difference, the Chan and Zhang (1999) method will be used.

These analyses will also be performed on all post-baseline visits.

Sponsor:	Ocular Therapeutix, Inc.		
Protocol:	CLN-Protocol-0054		
Document Version No.:	V1.0 Document Date: 01-OCT		01-OCT-2021

6. **REFERENCES**

American Academy of Ophthalmology Cornea/External Disease Panel. Preferred Practice Pattern[®] Guidelines. Dry Eye Syndrome. San Francisco, CA: American Academy of Ophthalmology; 2018. Available at www.aao.org/ppp. Accessed September 23, 2019.

- Disease in the United States Among Adults Aged 18 Years and Older. Am J Ophthalmol. Oct;182:90-98.
- Perry HD. Dry eye disease: Pathophysiology, classification, and diagnosis. Am J Manag Care. 2008;14:S79-S87.
- Schultz C. Safety and efficacy of cyclosporine in the treatment of chronic dry eye. Ophthalmol Eye Dis. 2014;6:37-42.

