approximately 0.36 mg of cyclosporine and is designed to deliver therapeutic levels of cyclosporine onto the ocular surface for a duration of approximately 12 weeks. Continuous release of cyclosporine from the hydrogel inserts may result in higher daily concentrations of cyclosporine delivered to the ocular surface than is found with topical Restasis. In a beagle dog study, the average cyclosporine release rate from OTX-CSI was 3.5 μ g/day, exceeding the estimated daily bioavailable dose from Restasis of <1.4 μ g cyclosporine per day. Tear fluid concentrations of cyclosporine measured in the beagle dog studies were typically 1 to 3 μ g/mL. It is known that cyclosporine accumulates with repeat dosing in the cornea and lacrimal gland in animal studies (Acheampong et al, 1999), and this may be the case with sustained cyclosporine delivery from OTX-CSI. However, considering the low cyclosporine concentrations required at the ocular surface, OTX-CSI, offers promise as a potential sustained release treatment for patients with signs and symptoms of DED for approximately 12 weeks with a single insert.

The two active formulations of OTX-CSI being studied in this clinical trial contain the same cyclosporine dose and release drug at the same daily rates but differ in their hydrogel composition. These two formulations are designed to have different breakdown periods of the hydrogel with one formulation designed to last approximately 2 to 3 months (Formulation 1) and the other approximately 3 to 4 months (Formulation 2A). These formulations have been evaluated in prior human clinical trials conducted by the sponsor either with an active molecule or in a non-significant risk (NSR) study. The difference between these two OTX-CSI hydrogel formulations will be studied for retention and persistence in this Phase 1/2 clinical study.

The two HV insert formulations being studied contain no active drug but differ in their hydrogel formulation. These two formulations are designed to have different hydrogel breakdown periods with one formulation designed to last approximately 1 week (Formulation 3) and the other approximately 3 to 4 months (Formulation 2B). The difference between these two HV formulations will be studied in the clinical study as they provide for a short-acting and long-acting placebo.

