6.2.2.3 Exploratory Efficacy Endpoints

- Tear Film Break Up Time (TBUT), CFB at Week 12
- Presence of OTX-CSI or HV insert at all post-baseline visits
- Ease of insertion as assessed by the Investigator
- Ease of visualization as assessed by the Investigator

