11 STATISTICAL METHODS AND DATA ANALYSIS

11.1 Statistical Methods

Summaries for continuous variables will include the sample size, mean, standard deviation, median, minimum, and maximum. Summaries for discrete variables will include frequencies and percentages. The baseline visit will be defined as the last non-missing measure prior to initiation of investigational treatment. Differences between treatment groups will be calculated as OTX-CSI minus HV and change from baseline will be calculated as follow-up visit minus baseline visit values.

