11.8 Exploratory Analyses

Tear Film Break Up Time at Week 12 will be analyzed similar to the Schirmer Test, however only observed data will be used. Presence of insert, ease of insertion as assessed by the Investigator and ease of visualization as assessed by the Investigator at all post-baseline visits will be summarized using discrete statistics and will be tested between treatment groups (all treatment groups separately and combined) using the Pearson chi-squared statistic.

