11.9 Reporting Deviations

Should there be changes in any analyses described in the protocol, the statistical analysis plan will document them. Should there be changes in any analyses described in the statistical analysis plan, the final clinical study report will describe them.

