The rest of secondary efficacy endpoint analysis of below parameters will be done similar to analysis of Schirmer test using observed data, for each post-baseline visit (Visit 3, Visit 4, Visit 5, Visit 6, Visit 7, Visit 8, and 30-Day Follow-Up) on mITT and PP populations using observed data:

1. Conjunctival Lissamine Green Staining using NEI scale

2. Ocular Surface Disease Index questionnaire (OSDI©) (total score, each of the three domains and the individual questions)

3. SPEED measures (overall score and individual questions) and its CFB

4.7.4. **Exploratory Analyses**

The exploratory analyses will be done on mITT populations for both study and non-study eye.

The Tear Film Break Up Time at Week 12 and its CFB will be summarized using descriptive statistics (the number of subjects, mean, SD, median, minimum and maximum) by treatment group and overall. Tear Film Break Up Time at Week 12 will be analyzed similar to analysis of Schirmer test using observed data.

Ease of insertion as assessed by the Investigator at Visit 2 or Visit 2B, presence of insert and ease of visualization as assessed by the Investigator at all post-baseline visits will be summarized using discrete statistics (number and percentage) and will be tested between treatment groups (CSI Formulation 1 to HV Formulation 2B, CSI Formulation 2A to HV Formulation 2B, CSI Formulation 1 to HV Formulation 3, CSI Formulation 2A to HV Formulation 3, will be reported. This model will also be used to compare overall OTX-CSI (combined Formulation 1 and Formulation 2A) to each HV Formulation (2B and 3). To analyze ease of insertion as assessed by the Investigator and ease of visualization as assessed by the Investigator, Pearson Chi-squared test will be used. To analyze presence of insert, Fisher's exact Test will be used.

Sponsor:	Ocular Therapeutix, Inc.		
Protocol:	CLN-Protocol-0054		
Document Version No.:	V1.0 Document Date: 01-OCT-2021		

4.8. **Pharmacokinetic Evaluations**

PK analysis will be described separately.

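### The SAP drops the Formulation 1 v Formulation 2A comparison of insert persistence that the protocol names as a study purpose, and plans no estimate or confidence interval for it

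*SAP*

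**What the plan says.** **Protocol.** Section 4.2 describes two active inserts with the same dose and daily release but different hydrogels, designed to last about 2 to 3 months (F1) and 3 to 4 months (F2A). It then states: "The difference between these two OTX-CSI hydrogel formulations will be studied for retention and persistence in this Phase 1/2 clinical study". It says the same of the vehicles in general terms: "The difference between these two HV formulations will be studied in the clinical study". Section 4.5 gives adequate retention and persistence, for about 12 weeks of delivery, as the purpose of studying both active formulations. The matching endpoint is exploratory (6.2.2.3): "Presence of OTX-CSI or HV insert at all post-baseline visits". Under 11.8, presence "will be tested between treatment groups (all treatment groups separately and combined) using the Pearson chi-squared statistic". Section 11.1 defines the direction of comparisons: "Differences between treatment groups will be calculated as OTX-CSI minus HV". On changes, 11.9 says: "Should there be changes in any analyses described in the protocol, the statistical analysis plan will document them".

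**SAP.** Section 5 states: "The difference between two OTX-CSI hydrogel formulations as well as the difference between two HV formulations will not be studied". It gives no reason, and says that the SAP prevails over the protocol. Under 4.7.4, presence is summarised as number and percentage at every post-baseline visit, and "will be tested between treatment groups (CSI Formulation 1 to HV Formulation 2B, CSI Formulation 2A to HV Formulation 2B", followed by F1 v HV 3, F2A v HV 3, and pooled OTX-CSI v each vehicle. Presence is tested with Fisher's exact test. Tables 14.2.4.3.1 and 14.2.4.3.2 report presence by eye, Listing 16.1.14 gives it by subject, and Table 14.1.8 summarises exposure.

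**The concern.** F1 v F2A is the only randomised comparison of two hydrogels that both carry the drug. The protocol says that it will be made, and the SAP removes it without explanation. None of the planned contrasts replaces it, because each sets an active arm against a vehicle. F1 v HV 2B differs in drug content as well as hydrogel.

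What is at stake is limited. A reader who wants the answer to the protocol's own question must either calculate it after the event or infer it from two separate vehicle tests, and that inference can mislead. A contrast fixed before unmasking, with an interval, would carry more weight.

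**Working it through.** The plan states no power, retention rate or expected difference for this comparison, so there is no figure of its own to reproduce. As a consistency check, 140 subjects split 2:2:2:1 gives 40, 40, 40 and 20, which matches the arm table.

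**1. Is F1 v F2A covered anywhere in the SAP?**

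| Place | Content | F1 v F2A difference or CI? |
|---|---|---|
| SAP 4.7.4 | F1, F2A and pooled OTX-CSI, each v HV 2B and v HV 3 | No |
| Tables 14.2.4.3.1 and 14.2.4.3.2 | Presence by eye | Per-arm counts only |
| SAP 4.6, Table 14.1.8 | Exposure in days by treatment group and overall | Descriptive only |
| SAP 5 and 7.3.8 | Chan and Zhang interval | For the Schirmer 10 mm response, not for presence |

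Exposure is a weak substitute. It uses the Safety set, which adds Cohort 1 (about 5 subjects, all F2A). Protocol 8.3.11 allows inserts to be replaced in the first six weeks in that cohort only. SAP 4.6 does not say that the main summary is split by cohort.

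**2. Can the two vehicle tests stand in for the direct contrast?** A constructed example, with counts chosen to show the problem: present in 19/40 (F1), 25/40 (F2A) and 29/40 (HV 2B).

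- F1 v HV 2B: Fisher p = 0.039.
- F2A v HV 2B: Fisher p = 0.47.
- F2A minus F1: 25/40 − 19/40 = 6/40 = 15 points, Chan-Zhang 95% CI −7.4 to 36.4, Fisher p = 0.26.

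One vehicle test is significant and the other is not, yet the direct evidence is inconclusive.

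**3. How precise would the direct estimate be?** The presence rates are assumptions, with 40 per arm and one eye per subject. The Wald half-width is 1.96 × √[2p(1−p)/40]; the Chan-Zhang figure is the exact one.

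| Presence in both arms | Wald half-width | Chan-Zhang half-width |
|---|---|---|
| 50% | 21.9 points | 22.8 points |
| 80% | 17.5 points | 18.2 points |
| 90% | 13.1 points | 15.5 points |

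**4. What could it detect?** Exact two-sided Fisher power at 0.05 is 75% for 50% v 80% and 37% for 50% v 70%. With an assumed 15% loss (34 v 34) it falls to 68% and 32%.

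**5. Which visits are informative?** At about 4.35 weeks to the month, the designed lifetimes are about 9 to 13 weeks (F1) and 13 to 17 weeks (F2A). Weeks 2, 4 and 6 precede both ranges and Week 9 is at the start of F1's. Weeks 12 and 16 are where the two should separate, and Week 12 also matches the delivery aim in protocol 4.5.

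**6. Which eyes should count?** SAP 3.1 defines mITT by subject, and protocol 7.4 keeps subjects with one successful insertion. Without an eye-level rule, an eye that never received an insert could count as not present, which would mix placement failure with loss of the insert.

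**The case against.** The strongest reply is that no rule was broken. Protocol 11.9 asks only that the SAP document changes, and section 5 does so. The sentence in protocol 4.2 stands in a rationale section. The objectives name safety, tolerability and efficacy, and saying that a difference will be studied promises neither a test nor an interval. The counts for F1 and F2A appear in the same table, so the difference is one subtraction. Nothing in the SAP proposes to infer F1 v F2A from two vehicle p-values. All of this stands, and it is why the point is minor.

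A reader might infer more: that the SAP hides a contradiction, or that protocol 11.8 committed the trial to testing F1 v F2A. The documents support neither. The change is disclosed under its own heading. The wording of 11.8 on separate and combined groups could include the contrast, but read with the active-minus-vehicle definition in 11.1 it can equally mean active against vehicle only.

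What survives is narrower. The protocol gives persistence as the reason for two active arms, and the plan contains no estimate, with its uncertainty, of how they differ. A subtraction from the table gives no interval and is not prespecified. A sentence of explanation in section 5 would help the record but would not supply the estimate.

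**Conclusion.** The concern holds as a minor gap on an exploratory endpoint. A comparison that the protocol says will be made has been dropped openly but without a reason, and no F1 v F2A estimate or interval for insert presence is planned. No primary or secondary result is affected, and the per-arm counts and listings remain. It would be wrong to conclude that the trial can say nothing about the two hydrogels: each arm can still be described.

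The precision figures rest on assumed presence rates, because the documents give none, and on 40 assessed eyes per arm. On that basis the interval would be about ±16 to ±23 points at equal rates of 90% to 50%. It could show a large difference but would leave moderate ones uncertain.

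**What to change.** In SAP section 5, replace the quoted sentence with:

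> The difference between the two OTX-CSI formulations will be studied for insert presence only (Section 4.7.4). The difference between the two HV formulations will not be studied.

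In SAP 4.7.4, add:

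> Insert presence will also be compared between CSI Formulation 2A and CSI Formulation 1 at Week 12 (main) and Week 16 (supportive), study and non-study eye separately, as the difference in proportion present (F2A minus F1) with a Chan and Zhang 95% CI, in Cohort 2 mITT eyes in which an insert was successfully placed at Visit 2 or 2B. An eye whose insert was removed counts as not present from removal onward. Eyes not assessed at a visit are left out of that visit, and their number is shown by arm. The comparison is exploratory and unadjusted.

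Show the result in Tables 14.2.4.3.1 and 14.2.4.3.2. Earlier visits stay as per-arm counts, and all planned tests are kept. The change should be made before unmasking.

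**Cost.** No new data are needed. The SAP 7.3.8 code is written for the Schirmer response across all arms, so it must be pointed at presence and restricted to F1 and F2A. There are 2 visits × 2 eyes = 4 more unadjusted comparisons. If these were independent, each with a 5% error rate, the chance of at least one interval falsely excluding zero would be 1 − 0.95⁴ = 19%. Eyes and visits are correlated and the exact interval is conservative, so the true figure is lower.

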7. CLINICAL STUDY REPORT APPENDICES

7.1. Statistical Tables to be Generated

- Table 14.1.1: Overall Disposition and Subject Accountability All Subjects Screened
- Table 14.1.2: Overview of Analysis Sets
- Table 14.1.3: Major Protocol Deviations mITT and Cohort 1
- Table 14.1.4: Demographic and Baseline Characteristics mITT and Cohort 1
- Table 14.1.5: Ocular Characteristics at baseline mITT and Cohort 1
- Table 14.1.6.1: Study Eye Ocular Medical History mITT and Cohort 1
- Table 14.1.6.2: Non-Study Eye Ocular Medical History mITT and Cohort 1
- Table 14.1.6.3: Non-ocular Medical History mITT and Cohort 1
- Table 14.1.7.1: Study Eye Ocular Prior Medications SAFETY
- Table 14.1.7.2: Non-Study Eye Ocular Prior Medications SAFETY
- Table 14.1.7.3: Non-ocular Prior Medications SAFETY
- Table 14.1.7.4: Study Eye Ocular Concomitant Medications SAFETY
- Table 14.1.7.5: Non-Study Eye Ocular Concomitant Medications SAFETY
- Table 14.1.7.6: Non-ocular Concomitant Medications SAFETY
- Table 14.1.8: Treatment Exposure SAFETY
- Table 14.2.1.1.1: The Summary and Linear Model with MCMC Multiple Imputation of Change from Baseline in Schirmer Test (mm) on Study Eye at Visit 7 (Week 12) and other Post-Baseline Visits mITT
- Table 14.2.1.1.2: The Summary and Linear Model with MCMC Multiple Imputation of Change from Baseline in Schirmer Test (mm) on Study Eye at Visit 7 (Week 12) and other Post-Baseline Visits PP
- Table 14.2.1.1.3: The Summary and Linear Model with MCMC Multiple Imputation of Change from Baseline in Schirmer Test (mm) on Non-Study Eye at Visit 7 (Week 12) and other Post-Baseline Visits mITT
- Table 14.2.1.1.4: The Summary and Linear Model with MCMC Multiple Imputation of Change from Baseline in Schirmer Test (mm) on Non-Study Eye at Visit 7 (Week 12) and other Post-Baseline Visits PP

Sponsor:	Ocular Therapeutix, Inc.		
Protocol:	CLN-Protocol-0054		
Document Version No.:	V1.0	Document Date:	01-OCT-2021

- Table 14.2.2.1.1: The Summary and Linear Model with Last Observation Carried Forward (LOCF) of Change from Baseline in Schirmer Test (mm) on Study Eye at Visit 7 (Week 12) and other Post-Baseline Visits mITT
- Table 14.2.2.1.2: The Summary and Linear Model with Last Observation Carried Forward (LOCF) of Change fromBaseline in Schirmer Test (mm) on Study Eye at Visit 7 (Week 12) and other Post-Baseline Visits PP
- Table 14.2.2.1.3: The Summary and Linear Model with Last Observation Carried Forward (LOCF) of Change from Baseline in Schirmer Test (mm) on Non-Study Eye at Visit 7 (Week 12) and other Post-Baseline Visits – mITT
- Table 14.2.2.1.4: The Summary and Linear Model with Last Observation Carried Forward (LOCF) of Change fromBaseline in Schirmer Test (mm) on Non-Study Eye at Visit 7 (Week 12) and other Post-Baseline Visits PP
- Table 14.2.2.2.1: The Summary and Linear Model of Change from Baseline in Schirmer Test (mm) on Study Eye at Visit 7 (Week 12) and other Post-Baseline Visits mITT (Observed data)
- Table 14.2.2.2.2: The Summary and Linear Model of Change from Baseline in Schirmer Test (mm) on Study Eye at Visit 7 (Week 12) and other Post-Baseline Visits PP (Observed data)
- Table 14.2.2.2.3: The Summary and Linear Model of Change from Baseline in Schirmer Test (mm) on Non-Study Eye at Visit 7 (Week 12) and other Post-Baseline Visits mITT (Observed data)
- Table 14.2.2.2.4: The Summary and Linear Model of Change from Baseline in Schirmer Test (mm) on Non-Study Eye at Visit 7 (Week 12) and other Post-Baseline Visits PP (Observed data)
- Table 14.2.2.3.1: The Summary and Linear Model with Fully Conditional Specification (FCS) Multiple Imputation of Change from Baseline in Schirmer Test (mm) on Study Eye at Visit 7 (Week 12) and other Post-Baseline Visits – mITT
- Table 14.2.2.3.2: The Summary and Linear Model withFully Conditional Specification (FCS) Multiple Imputation of Change from Baseline in Schirmer Test (mm) on Study Eye at Visit 7 (Week 12) and other Post-Baseline Visits – PP
- Table 14.2.2.3.3: The Summary and Linear Model withFully Conditional Specification (FCS) Multiple Imputation of Change from Baseline in Schirmer Test (mm) on Non-Study Eye at Visit 7 (Week 12) and other Post-Baseline Visits – mITT
- Table 14.2.2.3.4: The Summary and Linear Model withFully Conditional Specification (FCS) Multiple Imputation of Change from Baseline in Schirmer Test (mm) on Non-Study Eye at Visit 7 (Week 12) and other Post-Baseline Visits – PP
- Table 14.2.3.1.1: Percent of eyes with ≥10 mm Increase in Schirmer Test from Baseline Using Fully Conditional Specification (FCS) Multiple Imputation on Study Eye at visit 7 (Week 12) and other Post-Baseline Visits mITT
- Table 14.2.3.1.2: Percent of eyes with ≥10 mm Increase in Schirmer Test from Baseline Using Fully Conditional Specification (FCS) Multiple Imputation on Study Eye at visit 7 (Week 12) and other Post-Baseline Visits PP

Sponsor:	Ocular Therapeutix, Inc.		
Protocol:	CLN-Protocol-0054		
Document Version No.:	V1.0	Document Date:	01-OCT-2021

- Table 14.2.3.1.3: Percent of eyes with ≥10 mm Increase in Schirmer Test from Baseline Using Fully Conditional Specification (FCS) Multiple Imputation on Non-Study Eye at visit 7 (Week 12) and other Post-Baseline Visits mITT
- Table 14.2.3.1.4: Percent of eyes with ≥10 mm Increase in Schirmer Test from Baseline Using Fully Conditional Specification (FCS) Multiple Imputation on Non-Study Eye at visit 7 (Week 12) and other Post-Baseline Visits PP
- Table 14.2.3.2.1: Percent of eyes with ≥10 mm Increase in Schirmer Test from Baseline Using Last Observation Carried Forward (LOCF) on Study Eye at visit 7 (Week 12) and other Post-Baseline Visits – mITT

Table 14.2.3.2.2: Percent of eyes with ≥10 mm Increase in Schirmer Test from Baseline Using Last Observation Carried Forward (LOCF) on Study Eye at visit 7 (Week 12) and other Post-Baseline Visits – PP

Table 14.2.3.2.3: Percent of eyes with ≥10 mm Increase in Schirmer Test from Baseline Using Last Observation Carried Forward (LOCF) on Non-Study Eye at visit 7 (Week 12) and other Post-Baseline Visits – mITT

Table 14.2.3.2.4: Percent of eyes with ≥10 mm Increase in Schirmer Test from Baseline Using Last Observation Carried Forward (LOCF) on Non-Study Eye at visit 7 (Week 12) and other Post-Baseline Visits – PP

Table 14.2.3.3.1: Percent of eyes with ≥10 mm Increase in Schirmer Test from Baseline on Study Eye at visit 7 (Week 12) and other Post-Baseline Visits – mITT (Observed data)

Table 14.2.3.3.2: Percent of eyes with ≥10 mm Increase in Schirmer Test from Baseline on Study Eye at visit 7 (Week 12) and other Post-Baseline Visits – PP (Observed data)

Table 14.2.3.3.3: Percent of eyes with ≥10 mm Increase in Schirmer Test from Baseline on Non-Study Eye at visit 7 (Week 12) and other Post-Baseline Visits – mITT (Observed data)

Table 14.2.3.3.4: Percent of eyes with ≥10 mm Increase in Schirmer Test from Baseline on Non-Study Eye at visit 7 (Week 12) and other Post-Baseline Visits – PP (Observed data)

Table 14.2.3.4.1: The Summary and Linear Model with MCMC Multiple Imputation of Change from Baseline in Eye Dryness Severity and Frequency Scores (VAS) at each Post-Baseline Visits – mITT

Table 14.2.3.4.2: The Summary and Linear Model with MCMC Multiple Imputation of Change from Baseline in Eye Dryness Severity and Frequency Scores (VAS) at each Post-Baseline Visits – PP

- Table 14.2.3.5.1: The Summary and Linear Model with Last Observation Carried Forward (LOCF) of Change from Baseline in Eye Dryness Severity and Frequency Scores (VAS) at each Post-Baseline Visits mITT
- Table 14.2.3.5.2: The Summary and Linear Model with Last Observation Carried Forward (LOCF) of Change from Baseline in Eye Dryness Severity and Frequency Scores (VAS) at each Post-Baseline Visits PP

Table 14.2.3.6.1: The Summary and Linear Model of Change from Baseline in Eye Dryness Severity and Frequency Scores (VAS) at each Post-Baseline Visits – mITT (Observed data)

Sponsor:	Ocular Therapeutix, Inc.		
Protocol:	CLN-Protocol-0054		
Document Version No.:	V1.0	Document Date:	01-OCT-2021

- Table 14.2.3.6.2: The Summary and Linear Model of Change from Baseline in Eye Dryness Severity and Frequency Scores (VAS) at each Post-Baseline Visits PP (Observed data)
- Table 14.2.3.7.1: The Summary and Linear Model with Fully Conditional Specification (FCS) Multiple Imputation of Change from Baseline in Eye Dryness Severity and Frequency Scores (VAS) at each Post-Baseline Visits mITT
- Table 14.2.3.7.2: The Summary and Linear Model with Fully Conditional Specification (FCS) Multiple ImputationChange from Baseline in Eye Dryness Severity and Frequency Scores (VAS) at each Post-Baseline Visits PP
- Table 14.2.3.8.1: The Summary and Linear Model with MCMC Multiple Imputation of Change from Baseline in Corneal Fluorescein Staining (CFS) and its Sub-Regions on Study Eye at each Post-Baseline Visits mITT
- Table 14.2.3.8.2: The Summary and Linear Model with MCMC Multiple Imputation of Change from Baseline in Corneal Fluorescein Staining (CFS) and its Sub-Regions on Study Eye at each Post-Baseline Visits PP
- Table 14.2.3.8.3: The Summary and Linear Model with MCMC Multiple Imputation of Change from Baseline in Corneal Fluorescein Staining (CFS) and its Sub-Regions on Non-Study Eye at each Post-Baseline Visits mITT
- Table 14.2.3.8.4: The Summary and Linear Model with MCMC Multiple Imputation of Change from Baseline in Corneal Fluorescein Staining (CFS) and its Sub-Regions on Non-Study Eye at each Post-Baseline Visits PP
- Table 14.2.3.9.1: The Summary and Linear Model with Last Observation Carried Forward (LOCF) of Change from Baseline in Corneal Fluorescein Staining (CFS) and its Sub-Regions on Study Eye at each Post-Baseline Visits – mITT
- Table 14.2.3.9.2: The Summary and Linear Model with Last Observation Carried Forward (LOCF) of Change from Baseline in Corneal Fluorescein Staining (CFS) and its Sub-Regions on Study Eye at each Post-Baseline Visits PP
- Table 14.2.3.9.3: The Summary and Linear Model with Last Observation Carried Forward (LOCF) of Change from Baseline in Corneal Fluorescein Staining (CFS) and its Sub-Regions on Non-Study Eye at each Post-Baseline Visits mITT
- Table 14.2.3.9.4: The Summary and Linear Model with Last Observation Carried Forward (LOCF) of Change from Baseline in Corneal Fluorescein Staining (CFS) and its Sub-Regions on Non-Study Eye at each Post-Baseline Visits – PP
- Table 14.2.3.10.1: The Summary and Linear Model of Change from Baseline in Corneal Fluorescein Staining (CFS) and its Sub-Regions on Study Eye at each Post-Baseline Visits mITT (Observed data)
- Table 14.2.3.10.2: The Summary and Linear Model of Change from Baseline in Corneal Fluorescein Staining (CFS) and its Sub-Regions on Study Eye at each Post-Baseline Visits PP (Observed data)
- Table 14.2.3.10.3: The Summary and Linear Model of Change from Baseline in Corneal Fluorescein Staining (CFS) and its Sub-Regions on Non-Study Eye at each Post-Baseline Visits mITT (Observed data)
- Table 14.2.3.10.4: The Summary and Linear Model of Change from Baseline in Corneal Fluorescein Staining (CFS) and its Sub-Regions on Non-Study Eye at each Post-Baseline Visits PP (Observed data)

Sponsor:	Ocular Therapeutix, Inc.		
Protocol:	CLN-Protocol-0054		
Document Version No.:	V1.0	Document Date:	01-OCT-2021

Table 14.2.3.11.1: The Summary and Linear Model with Fully Conditional Specification (FCS) Multiple Imputation of Change from Baseline in Corneal Fluorescein Staining (CFS) and its Sub-Regions on Study Eye at each Post-Baseline Visits – mITT

- Table 14.2.3.12.1: The Summary and Linear Model of Change from Baseline in Total Conjunctival Lissamine Green Staining (CLGS) on Study Eye at each Post-Baseline Visits mITT
- Table 14.2.3.12.2: The Summary and Linear Model of Change from Baseline in Total Conjunctival Lissamine Green Staining (CLGS) on Study Eye at each Post-Baseline Visits PP
- Table 14.2.3.12.3: The Summary and Linear Model of Change from Baseline in Total Conjunctival Lissamine Green Staining (CLGS) on Non-Study Eye at each Post-Baseline Visits mITT
- Table 14.2.3.12.4: The Summary and Linear Model of Change from Baseline in Total Conjunctival Lissamine Green Staining (CLGS) on Non-Study Eye at each Post-Baseline Visits PP
- Table 14.2.3.13.1: The Summary of Ocular Surface Disease Index (OSDI) individual questions by Visit mITT
- Table 14.2.3.13.2: The Summary of Ocular Surface Disease Index (OSDI) individual questions by Visit PP
- Table 14.2.3.14.1: The Summary and Linear Model of Change from Baseline in Ocular Surface Disease Index (OSDI), its domains, and individual questions at each Post-Baseline Visits mITT
- Table 14.2.3.14.2: The Summary and Linear Model of Change from Baseline in Ocular Surface Disease Index (OSDI), its domains, and individual questions at each Post-Baseline Visits PP
- Table 14.2.3.15.1: The Summary of Individual Questions of First Section of Standard Patient Evaluation of Eye Dryness (SPEED) (Symptoms You Experience And When They Occur) By Visit mITT
- Table 14.2.3.15.2 The Summary of Individual Questions of First Section of Standard Patient Evaluation of Eye Dryness (SPEED) (Symptoms You Experience And When They Occur) By Visit PP
- Table 14.2.3.15.3: The Summary of Individual Questions of Second And Third Sections of Standard Patient Evaluation of Eye Dryness (SPEED) (Frequency And Severity Of Symptoms) by Visit – mITT

Table 14.2.3.11.2: The Summary and Linear Model with Fully Conditional Specification (FCS) Multiple Imputation of Change from Baseline in Corneal Fluorescein Staining (CFS) and its Sub-Regions on Study Eye at each Post-Baseline Visits – PP

Table 14.2.3.11.3: The Summary and Linear Model with Fully Conditional Specification (FCS) Multiple Imputation of Change from Baseline in Corneal Fluorescein Staining (CFS) and its Sub-Regions on Non-Study Eye at each Post-Baseline Visits – mITT

Table 14.2.3.11.4: The Summary and Linear Model with Fully Conditional Specification (FCS) Multiple Imputation of Change from Baseline in Corneal Fluorescein Staining (CFS) and its Sub-Regions on Non-Study Eye at each Post-Baseline Visits – PP

Sponsor:	Ocular Therapeutix, Inc.		
Protocol:	CLN-Protocol-0054		
Document Version No.:	V1.0	Document Date:	01-OCT-2021

- Table 14.2.3.15.4 The Summary of Individual Questions of Second and Third Sections of Standard Patient Evaluation of Eye Dryness (SPEED) (Frequency and Severity of Symptoms) by Visit PP
- Table 14.2.3.16.1: The Summary and Linear Model of Change from Baseline inStandard Patient Evaluation of Eye Dryness (SPEED) total score and its individual questions at each Post-Baseline Visits mITT
- Table 14.2.3.16.2: The Summary and Linear Model of Change from Baseline inStandard Patient Evaluation of Eye Dryness (SPEED) total score and its individual questions at each Post-Baseline Visits PP
- Table 14.2.4.1.1: The Summary and Linear Model of Change from Baseline in TFBUT average on Study Eye at Visit 7 (Week 12) mITT
- Table 14.2.4.1.2: The Summary and Linear Model of Change from Baseline in TFBUT average on Non-Study Eye at Visit 7 (Week 12) mITT
- Table 14.2.4.2.1: Ease of Insertion as Assessed by the Investigator on Study Eye at Visit 2 (or Visit 2B) mITT
- Table 14.2.4.2.2: Ease of Insertion as Assessed by the Investigator on Non-Study Eye at Visit 2 (or Visit 2B) mITT
- Table 14.2.4.3.1: The Presence of Insert on Study Eye at each Post-Baseline Visits mITT
- Table 14.2.4.3.2: The Presence of Insert on Non-Study Eye at each Post Baseline-Visits mITT
- Table 14.2.4.4.1: Ease of Visualization as Assessed by Investigator on Study Eye at each Post-Baseline Visits mITT
- Table 14.2.4.4.2: Ease of Visualization as Assessed by Investigator on Non-Study Eye at each Post-Baseline Visits mITT
- Table 14.3.1: Overview of Treatment-Emergent Adverse Events (TEAEs) SAFETY
- Table 14.3.2.1: Ocular Treatment-Emergent Adverse Events (TEAEs) by System Organ Class and Preferred Term SAFETY
- Table 14.3.2.2: Non-Ocular Treatment-Emergent Adverse Events (TEAEs) by System Organ Class and Preferred Term SAFETY
- Table 14.3.2.3: Ocular Treatment-Emergent Adverse Events (TEAEs) by Preferred Term
- Table 14.3.2.4: Non-Ocular Treatment-Emergent Adverse Events (TEAEs) by Preferred Term
- Table 14.3.3.1: Ocular Serious Treatment-Emergent Adverse Events (TEAEs) by System Organ Class and Preferred Term SAFETY
- Table 14.3.3.2: Non-Ocular Serious Treatment-Emergent Adverse Events (TEAEs) by System Organ Class and Preferred Term – SAFETY
- Table 14.3.4.1: Ocular Treatment-Emergent Adverse Events (TEAEs) Related to IP by System Organ Class and Preferred Term SAFETY

Sponsor:	Ocular Therapeutix, Inc.		
Protocol:	CLN-Protocol-0054		
Document Version No.:	V1.0	Document Date:	01-OCT-2021

- Table 14.3.4.2 Non-Ocular Treatment-Emergent Adverse Events (TEAEs) Related to IP by System Organ Class and Preferred Term – SAFETY
- Table 14.3.4.3: Ocular Serious Treatment-Emergent Adverse Events (TEAEs) Related to IP by System Organ Class and Preferred Term – SAFETY
- Table 14.3.4.4: Non-Ocular Serious Treatment-Emergent Adverse Events (TEAEs) Related to IP by System Organ Class and Preferred Term – SAFETY
- Table 14.3.5.1: Maximum Severity of Ocular Treatment-Emergent Adverse Events (TEAEs) by System Organ Class and Preferred Term – SAFETY
- Table 14.3.5.2: Maximum Severity of Non-Ocular Treatment-Emergent Adverse Events (TEAEs) by System Organ Class and Preferred Term – SAFETY
- Table 14.3.6.1: Summary of Best Corrected Visual Acuity (BCVA) LogMAR VA Score and Change from Baseline on Study Eye by Visit SAFETY
- Table 14.3.6.2: Summary of Best Corrected Visual Acuity (BCVA) LogMAR VA Score and Change from Baseline on Non-Study Eye by Visit SAFETY
- Table 14.3.7.1: Summary of Intraocular Pressure (IOP) (mmHg), IOP ≥ 30 mmHg and Change from Baseline (CFB), CFB IOP >5 mmHg and >10 mmHg on Study Eye by Visit – SAFETY
- Table 14.3.7.2: Summary of Intraocular Pressure (IOP) (mmHg), IOP ≥ 30 mmHg and Change from Baseline (CFB), CFB IOP >5 mmHg and >10 mmHg on Non-Study Eye by Visit – SAFETY
- Table 14.3.8.1: Summary of Slit-Lamp Biomicroscopy Results on Study Eye by Location and Visit SAFETY
- Table 14.3.8.2: Summary of Slit-Lamp Biomicroscopy Results on Non-Study Eye by Location and Visit SAFETY
- Table 14.3.9.1: Summary of Fundus Examination Results on Study Eye by Visit SAFETY
- Table 14.3.9.2: Summary of Fundus Examination Results on Non-Study Eye by Visit SAFETY

Table 14.3.10: Summary of Artificial Tear Use from Baseline by Visit – SAFETY

